**A.6. Importance of the Proposed Research.** There is a clear scientific rationale and crucial need to take the next step and more comprehensively assess central and peripheral circadian rhythms in IBD in order to determine the impact of circadian misalignment in IBD on colonic mucosal inflammation, subclinical systemic inflammation, barrier function, and intestinal microbiota. In the proposed study, we will determine if patients with inactive UC have circadian misalignment of central and/or peripheral circadian rhythms and if they are more susceptible to circadian misalignment after a simulated night shift (Specific Aim 1) and determine if circadian misalignment impacts colonic barrier integrity and intestinal microbiota (Specific Aim 2). We selected UC as a model of IBD because: (1) it always affects the rectum/sigmoid, thus it is relatively easy to access and obtain the required colonic intestinal tissue through sigmoidoscopy, (2) microbiota-directed interventions like fecal microbiota transplant (FMT) appear to be more promising in UC than in CD, and (3) our data support that circadian misalignment has a substantial impact on the colonic barrier in UC subjects. The knowledge gained from the proposed studies is likely to lead to the identification of new mechanisms of how circadian misalignment promotes chronic inflammation in IBD, and allow for the study of new chronobiological therapeutics in IBD that target circadian misalignment such as bright light therapy, exogenous melatonin, or other molecular targets associated with circadian misalignment induced in IBD.

**Research Design:** 40 human subjects will be recruited into this proposed study: 20 Healthy Controls and 20 UC subjects with left sided inactive disease (Mayo Score  $\leq 2$ ) on stable medications. All subjects (UC and HC) will undergo a full medical history and physical examination including a blood draw for the screening visit. A urine drug screening will take place on the subject's first day at the sleep laboratory. Subjects who wish to participate will have the study explained by the coordinator and will then sign a Rush IRB-approved informed consent. All UC subjects will complete a validated questionnaire regarding disease-specific symptoms (Mayo Score) to determine they are inactive and may be enrolled in the study.

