**Sample Size Analysis:** All power estimates were computed using R package pwr, and we assume a Type I error rate of 0.05 and a 2-sided test for all analyses. Power estimates were derived from the data from my prior K grant. The primary endpoints of this study will be phase angle/DLMO (Aim 1) and colonic permeability (13-24h urinary sucralose) (Aim 2). For Aim 1, we found a  $\sim 2$ h phase advance in DLMO in NW compared to DW at -0.2 (SD=2.1) compared to -4.34 (SD=3.8), respectively. With a sample size of 20 in each group (10 men/10 women), this

provides an 86% power to detect differences in DLMO, but 98% power if sex is pooled. For Aim 2, we found a 40% increase in colonic permeability in night shift workers compared to day workers after moderate alcohol consumption at 0.57 compared to 0.11 (SD=0.20). With 20 subjects, this will give us a 84% power to detect a difference in colonic permeability between the two groups for each sex and if sex is pooled will give us a 97% power with a two-sided two-sample t-test at alpha=0.05 level. These conservative estimates provide a good estimate of the power to detect differences in phase angle and colonic permeability between UC patients before and after simulated night shifts. We anticipate we will have nonparametric data and will use the Wilcoxon match-pair test for analysis of colonic permeability, inflammatory cytokines, and markers of endotoxemia. Order effects will be used as a covariate in multivariate analysis with analysis of variance (ANOVA) and linear regression as indicated. Microbiota data analysis is described above. Non-parametric analysis of actigraphy data will be analyzed with the nparACT package. In our periodogram analysis of time series data we will use Fast Fourier Transform Non-linear Least Squares (FFT-NLLS), a nonlinear least-squares algorithm of a times series typically used for luminescence data (149) and analyzed with Biodare software (150). Data will be presented as mean  $\pm$  SEM for variables that can be considered normally distributed (or median and range for variables not normally distributed). All analyses will use R (v.3.2.5), Biodare 2, and SPSS (SPSS Inc., Chicago, IL).

**Inclusion Criteria:** *Study will include individuals that are;*

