### Exploratory Outcome Measures:

- **Aim 1** – Colonic clock gene expression and Per2::Luc activity in colonic organoids over 24 hours in both groups and each condition
- **Aim 2** – RNA seq of colonic organoids every 2 hours for over 24 hours to identify key molecular and inflammatory pathways under circadian regulation
- **Aim 3**: Use body temperature to measure central circadian rhythm to see if it correlates with melatonin levels at baseline and after misalignment

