**Figure 1. Outcome Measures**

Aims	Outcome Measure	Test	Assessment	Statistical Test
Aim 1	Primary	Phase Angle of entrainment (DLMO – sleep onset)	Baseline	ANOVA
			Misalignment	
	Secondary	Clock gene expression in PBMCs	Baseline	Cosinor Analysis, Mixed Model ANOVA
			Misalignment	
Aim 2	Secondary	Urinary Melatonin	Baseline	Wilcoxon signed-rank test
			Misalignment	
	Exploratory	Clock gene expression and Per2::LUC in Colonic Organoids	Baseline	Cosinor Analysis, FFT-NLLS
			Misalignment	
Aim 2	Primary	Intestinal Permeability (i.e. 12-24 h Urinary Sucralfate)	Baseline	Mann-Whitney U test
			Misalignment	
	Secondary	Mayo Score (Endoscopy)	Baseline	Wilcoxon signed-rank test
			Misalignment	
	Secondary	Stool Calprotectin	Baseline	Wilcoxon signed-rank test
			Misalignment	
Aim 2	Secondary	Serum cytokines (IL-6, TNF- $\alpha$ )	Baseline	Repeated measures ANOVA
			Misalignment	
	Secondary	Fecal Microbiota	Baseline	Principal Coordinate Analysis
			Misalignment	
Aim 2	Secondary	Serum LBP, LPS, zonulin, sCD14, metabolomics	Baseline	Repeated measures ANOVA
			Misalignment	
	Exploratory	TER in 2D Colonic	Baseline	ANOVA

		Organoids with ex-vivo TNF- $\alpha$ /INF- $\gamma$	Misalignment	
Exploratory		RNA seq of Colonic Organoids	Baseline	JTK Cycle
			Misalignment	

**Safety and Adverse Events:** We have identified five key potential risks to human subjects in this study:

1. Risk to Confidentiality and Record-Keeping of patient personal health information (PHI).
2. Risk of potential side effects associated with Phlebotomy (blood draw).
3. Risk of potential side effects associated with Sigmoidoscopy and Colonic Biopsy.
4. Risk of potential side effects associated with completion of the Questionnaires.
5. Risk of potential side effects associated with in lab study

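### Organoid RNA-seq is assigned only JTK Cycle, which detects rhythm within one series; no test of a change in rhythm between conditions or groups is named, and the organoid clock-gene/Per2::LUC row has the same gap.

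*Combined protocol and SAP*

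**What the plan says.** Figure 1 (Outcome Measures) lists "RNA seq of Colonic Organoids" as exploratory, with assessments at Baseline and Misalignment and one statistical test, JTK Cycle. Exploratory Outcome Measures gives the purpose as "RNA seq of colonic organoids every 2 hours for over 24 hours to identify key molecular and inflammatory pathways under circadian regulation".

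The companion organoid outcome is "Colonic clock gene expression and Per2::Luc activity in colonic organoids over 24 hours in both groups and each condition". The Abstract places it (Aim 1c) among the assessments of whether UC patients are less resilient to misalignment than controls. Its Figure 1 row names "Cosinor Analysis, FFT-NLLS". The PBMC clock-gene row, by contrast, names "Cosinor Analysis, Mixed Model ANOVA".

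The Sample Size Analysis section says "we assume a Type I error rate of 0.05 and a 2-sided test for all analyses". It offers general comparative language, "Order effects will be used as a covariate in multivariate analysis with analysis of variance (ANOVA) and linear regression as indicated", and FFT-NLLS for time series. Section A.6 hopes that the work will lead to study of "molecular targets associated with circadian misalignment induced in IBD". The documents contain no test of a difference in phase, amplitude or presence of rhythm for RNA-seq, and no rule for multiplicity across genes.

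**The concern.** JTK Cycle ranks one series against cosine-shaped templates, and its null hypothesis is that the series has no rhythm. That suits a list of rhythmic genes within one condition. The hypothesis raised by assessing RNA-seq in two conditions, in a study of two groups, is a different one: that the rhythm is the same at baseline and after misalignment, or in UC and controls. No method in the RNA-seq row tests it.

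Cosinor and FFT-NLLS return estimates of period, phase and amplitude for each series. A second step is needed to compare those estimates between conditions and groups. The PBMC row names such a step and the organoid clock-gene/Per2::LUC row does not.

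At stake is what the exploratory organoid results can support. With only within-series tests in the plan, a statement that misalignment altered a gene's rhythm would have no planned error rate behind it. The informal substitute, noting which genes pass in one condition and fail in the other, can behave badly.

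**Working it through.** **Inputs.** From the documents: sampling every 2 h for over 24 h, taken as 13 points per series (0 to 24 h); the tests named in Figure 1; 20 subjects per group. Not given: how many subjects have organoid RNA-seq, the replicates per time point, the ratio of rhythm amplitude to noise, and the detection threshold. The plan states no power or error rate for this outcome, so there is no figure to reproduce.

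**Step 1: what each row provides.**

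| Figure 1 row | Within-series method | Comparative method |
|---|---|---|
| PBMC clock genes | Cosinor | Mixed model ANOVA |
| Organoid clock genes, Per2::LUC | Cosinor, FFT-NLLS | None named |
| Organoid RNA-seq | JTK Cycle | None named |

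**Step 2: closed form for comparing lists.** Suppose a gene has the same rhythm in both conditions and each series is detected independently with probability p. The chance that it is on exactly one list is 2p(1 − p).

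- p = 0.5: 2 × 0.5 × 0.5 = 50%
- p = 0.7: 2 × 0.7 × 0.3 = 42%
- p = 0.8: 2 × 0.8 × 0.2 = 32%
- p = 0.9: 2 × 0.9 × 0.1 = 18%
- p = 0.95: 2 × 0.95 × 0.05 = 9.5%

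The reference for discordance is not 5%. Two series with no rhythm, each tested at 5%, disagree in 2 × 0.05 × 0.95 = 9.5% of cases.

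**Step 3: simulation.** The settings were 20,000 genes per case, 13 points, one series per condition and normal noise. The JTK-type statistic was Kendall concordance with 24-h cosine templates, maximised over 12 phases, at nominal 0.05. The attained level was about 6% because the statistic is discrete. The comparator was a harmonic-regression F test of condition by (cosine, sine), with 2 and 20 degrees of freedom. The amplitude/SD ratios are assumptions.

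| Amplitude/SD | One list only, rhythm unchanged | Interaction test, rhythm unchanged | Interaction test, 12-h shift |
|---|---|---|---|
| 0.75 | 43% | 5% | 64% |
| 1 | 49% | 5% | 88% |
| 1.25 | 42% | 5% | 98% |
| 1.5 | 28% | 5% | 100% |
| 2 | 6% | 5% | 100% |
| 3 | 0.1% | 5% | 100% |

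The simulation agrees with the closed form. At ratio 1.5 the detection probability was 0.825, so 2 × 0.825 × 0.175 = 29%, against 28% simulated. The result depends on the threshold: a run with a slightly stricter one gave 39%, 49%, 36%, 11% and 0.3% at ratios 0.75, 1, 1.5, 2 and 3.

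**Step 4: phase.** List membership carries no information on phase. With a true 12-h shift the one-list-only share was 28.1%, against 28.4% with no shift, at ratio 1.5; at ratio 2 it was 6.4% against 6.1%. At ratio 2, 94% of shifted genes were on both lists. JTK Cycle also returns a best-fitting phase, however. Among shifted genes rhythmic in both conditions, that phase revealed the shift in 95% or more at ratio 1 and above.

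**The case against.** The strongest reply is that the stated RNA-seq aim is to find pathways under circadian regulation, which is rhythm detection, and JTK Cycle serves it. The wording about both groups and each condition belongs to the clock-gene/Per2::Luc outcome, and the sentence in A.6 looks ahead to future therapeutics without defining an RNA-seq contrast. This stands. It is why limiting the RNA-seq aim to rhythm detection would be an acceptable answer.

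Figure 1 is also shorthand: its fecal microbiota row names only an ordination. The general ANOVA and regression wording could be stretched to cover the organoids, and the reference list includes works on RNA-seq differential expression. The general wording is not tied to RNA-seq, however, the text does not cite those works, and a test of mean expression is not a test of rhythm.

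Four stronger readings are tempting and unsupported.

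- A reader might infer that changes will be read from overlapping lists. No section says so; the simulation shows only what would happen if they were.
- A reader might infer that phase shifts would be missed. JTK Cycle's phase estimates could show large shifts descriptively; what is missing is a planned test of them.
- A reader might infer that the protocol imposes a 12-h shift on organoid rhythms. Procedures shifts the behavioural cycle by 12 h, while Minimizing Risk says the design tries to keep circadian phase changes small. Nothing says that rhythms in culture are inverted.
- A reader might infer that the organoid findings would be mostly noise. That depends on amplitude, replication and threshold, none of which is given.

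The list argument does not apply to the clock-gene/Per2::LUC row, where the methods give continuous estimates. The gap there is only the missing comparison.

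**Conclusion.** The point holds as a gap in method. No between-condition or between-group test of rhythm, and no multiplicity rule, is specified for organoid RNA-seq, and JTK Cycle alone cannot supply one. The organoid clock-gene/Per2::LUC row lacks a comparative model although a two-group, two-condition comparison is intended.

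The cost of the informal substitute is conditional. If lists were compared, the share of unchanged genes appearing on one list only would run from about 50% at middling detection probability to near zero when detection is almost certain. An interaction test keeps that error at 5% throughout. These figures assume cosine-shaped rhythms, independent normal noise, 13 points and one series per condition. They do not model variation between donors.

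Both outcomes are exploratory. Primary and secondary conclusions are unaffected, and no data would be lost by settling the analysis now.

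**What to change.** - Keep JTK Cycle for describing which genes are rhythmic within a group and condition.
- For any baseline-versus-misalignment or UC-versus-control statement from RNA-seq, name a differential-rhythmicity model. One option is a 24-h harmonic regression per gene, with condition and group-by-condition interactions on the cosine and sine terms tested jointly. Take subject as the paired (random) unit and control the false discovery rate across genes. Other differential-rhythmicity methods would also serve.
- For organoid clock genes and Per2::Luc, compare per-subject cosinor or FFT-NLLS estimates in a mixed model with group, condition and their interaction, in line with the PBMC row.
- State that differences between JTK lists will not be interpreted as changes.
- Alternatively for RNA-seq, state that the aim is rhythm detection only and that no comparative claim will be made.

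The cost is a few lines in Figure 1 and the statistics text, and modest extra analysis. No new samples are needed. The harmonic model assumes roughly cosine-shaped rhythms, which is its main drawback.

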2c). The results of this innovative proposal will greatly increase our understanding of the important role circadian misalignment may have in UC disease activity and colonic inflammation, and identify new circadian regulated targets for treatment in UC.

**Objective:** The long-term objective of our research is to investigate the hypothesis that circadian misalignment worsens intestinal mucosal inflammation and disease course in IBD. Key evidence supporting this hypothesis include that disruption of circadian rhythms in the host impacts the intestinal barrier, microbiota composition, and mucosal/systemic immune function, all critical factors in the pathogenesis of IBD. Data from rodents generated by our group and others show that disruption of the light: dark cycle (a model of shift work) or genetic circadian rhythm disruption (of a core clock gene) changes the intestinal microbial community, alters the production of microbial products like short chain fatty acids (SCFAs) resulting in colonic hyperpermeability through disruption of the apical junctional complex (AJC) in colonic IECs, increased mucosal inflammation, culminating in a more pro-inflammatory state in the intestine. In humans, shift work increases susceptibility of the colonic barrier to an injurious agent like alcohol and increases systemic pro-inflammatory cytokines IL-6 and IL-1 $\beta$  and that chronic alterations in light:dark cycles in mouse models of IBD increase colitis severity and mortality. In humans with IBD, our group and others have shown that a later chronotype (Fig. 2A) and high variability in rest-activity rhythms (Fig. 2B) (both markers of circadian misalignment) are associated with worse IBD disease course, increased colonic permeability, alterations in the intestinal microbiota community (dysbiosis), and reduced colonic circadian clock gene expression. Therefore, the immediate goal of this proposal is to elucidate the mechanisms of colonic inflammation induced by circadian misalignment in UC. This will be the first comprehensive examination of human circadian rhythms in IBD.

**Hypothesis:** Circadian misalignment worsens intestinal mucosal inflammation and disease course in IBD.

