**Specific Aims:**

- Aim 1: Test the hypothesis that circadian misalignment is more prevalent in UC compared to healthy controls and that UC patients are more susceptible
- Aim 2: Test the hypothesis that circadian misalignment increases colonic permeability and mucosal inflammation through disrupting the AJC and adversely impacting microbial community structure / function in UC.

**Background:** A.1. IBD is Associated with Sleep Disruption. Crohn's Disease (CD) and Ulcerative Colitis (UC), collectively known as inflammatory bowel disease (IBD), are two devastating chronic diseases of the gastrointestinal tract (GIT). IBD is typically diagnosed at an early age, has no known cure, and has a chronic relapsing and remitting disease course that includes

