prevalence of shift work, and nighttime eating have made misalignment of our endogenous circadian rhythms more common. There are multiple causes for human circadian misalignment including shift work, long distance travel with jet lag, and perhaps the most common: social jet lag, which is changing the midpoint of sleep more than 2h between work and work-free days due to social obligations. The most well-studied model of circadian misalignment, shift work, is now estimated to include 15 million workers in the US. Not surprisingly, shift work is associated with a number of GIT disorders and diseases including irritable bowel syndrome, peptic ulcer disease, and colon cancer. Therefore, it is possible that circadian misalignment may be one factor that promotes intestinal inflammation and disease flare in UC.

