A.3. IBD is characterized by Intestinal Barrier Dysfunction and Inflammation. The intestinal barrier is the largest interface between the body and the environment and must be selectively permeable to restrict pro-inflammatory microbiota and microbial products but at the same time allow passage of nutrients, electrolytes, and water. Thus, integrity of the intestinal barrier is critical for maintaining good health. Indeed, disrupted intestinal barrier function (“leaky gut”), endotoxemia (i.e., high levels of systemic lipopolysaccharide (LPS)), and subsequent production of pro-inflammatory cytokines and reactive oxygen species are all hallmarks of IBD. In fact, fluctuations in intestinal barrier function in IBD is an established predictor of disease flare in CD and UC. Several environmental factors can disrupt the intestinal barrier function in IBD like medication, alcohol, and stress but this only occurs in a subset of individuals suggesting that resiliency of the intestine determines the impact of these environmental factors in chronic inflammatory disorders like IBD. The intestinal barrier consists of the apical junctional complex (AJC), both tight junction (TJ) and adherens junction (AJ) proteins, that links the IECs and seals the paracellular space to prevent translocation of pro-inflammatory bacteria and bacterial components such as LPS into the intestinal mucosa. IECs turnover every 4-5 days, replenished by a small population of intestinal stem cells (ISCs), and IEC regeneration and differentiation are essential to maintain barrier homeostasis. It has also been established that alterations in gut microbiota are another hallmark of IBD, and perturbation of the structure of the microbiome can disrupt the intestinal barrier and cause intestinal inflammation in IBD. Specifically, in IBD there is a decrease in bacterial diversity and temporal stability with a loss of bacteria in the Firmicutes phylum^79 and increase in Proteobacteria. It is not understood if alterations in the intestinal microbiota are the cause of or result from increased intestinal permeability and inflammation, but IBD is characterized by both barrier dysfunction and dysbiosis. Disruption of central or peripheral circadian rhythms is sufficient to impact both the intestinal barrier and the microbiota; therefore, it is important to determine if circadian misalignment is sufficient to induce changes in the GIT that promote intestinal inflammation and UC disease flare.

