
A.4. Circadian Rhythms are Critical to Maintain the Intestinal Barrier. Intestinal barrier homeostasis is mediated by cross-talk between IECs and the intestinal microbiota. This cross-talk occurs via multiple mechanisms including interactions with toll-like receptors (TLRs) on the IECs. There are multiple lines of evidence in cell lines, animal models, and human studies that support the scientific premise that disruption of circadian rhythms in the host negatively impacts intestinal barrier integrity: (1) alcohol (0.2%) increases the expression of the circadian clock genes Clock and Per2 in a human IEC line (Caco-2 cells), and knock down of Clock or Per2 gene expression by siRNA prevents alcohol-induced barrier dysfunction, (2) chronic disruption of the central clock by either disruption of light:dark cycles or a mutation in the core circadian molecular clock (i.e., Clock mutant mice) increases intestinal permeability and endotoxemia, (3) healthy night workers who consume alcohol (0.5g/kg daily for 7 days) have increased colonic permeability compared to healthy day workers consuming alcohol, and colonic permeability inversely correlates with decreased plasma melatonin over 24h, (4) our lab and others show that circadian misalignment in the host causes microbial alterations with a decrease in bacteria (Firmicutes) that produce short chain fatty acids (SCFA) like butyrate (Bu), and (5) the core clock machinery (Bmal1) regulates IEC cell regeneration and barrier homeostasis. Taken together, these studies strongly support the concept that circadian misalignment could promote IBD flare via a mechanism involving disrupting the colonic barrier and intestinal microbiota dysbiosis.

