Each potential subject will undergo an extensive screening procedure prior to participation in the study. The procedure begins with a telephone screening, involving a series of questions from a preliminary screening questionnaire and answering any questions potential subjects may have about the study. If the original preliminary telephone screening questionnaire reveals no grounds for exclusion (see "Inclusion/Exclusion Criteria" below), then potential subjects are asked to come to our clinic for a physical examination. These patients will all be interviewed by the study Clinical Coordinator and then get a full physical exam by the PI who is a licensed Gastroenterologist. Potential subjects will also complete several questionnaires to determine their suitability for study. Each potential subject is given a tour of the Clinical Chronobiology Center (CCC) in which they will live during the temporal isolation portion of the study. Every attempt will be made to acquaint each prospective subject with all of the procedures involved in this study in order to minimize the possible effect of uncertainty about the experimental procedures on the results. Written informed consent on an RUMC IRB-approved form will be obtained from each subject before his/her study begins. Each subject will be told that they will be free to discontinue participation in the experiment at any time and that the investigators also reserve the right to discontinue the study for medical or other reasons at any time.

**Early Withdrawal:** Participants may withdraw at any time.

**Procedures:** After consenting for the study all subjects: 1) Will be interviewed by a study coordinator and fill out detailed questionnaires so that we can collect demographic data, medical history, data on disease status and research questionnaires; 2) Will supply blood and urine samples (to assess the inclusion/exclusion criteria and to obtain baseline biological markers; 3) Will undergo an exam by PI [name] to assess the inclusion/exclusion criteria and to obtain baseline UC disease characteristics and have initial blood drawn/urine sample. 4) After interviews and exam and blood/urine analysis, as part of the screening process, eligible patients will be asked to continue participation and will be re-informed about the study.

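### The safety text does not name worsening of UC as a risk of the misalignment exposure, and the visible plan schedules no clinical contact with UC subjects after Day 7 discharge or after withdrawal following the Day 3 shift

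*Combined protocol and SAP*

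**What the plan says.** **Expected effect.** The Objective and Hypothesis sections state that "circadian misalignment worsens intestinal mucosal inflammation and disease course in IBD". Aim 2 will test whether "circadian misalignment increases colonic permeability and mucosal inflammation through disrupting the AJC". Background A.2 says "circadian misalignment may be one factor that promotes intestinal inflammation and disease flare in UC". Background A.3 says that "fluctuations in intestinal barrier function in IBD is an established predictor of disease flare in CD", and the sentence goes on to include UC. Background A.4 concludes that "circadian misalignment could promote IBD flare via a mechanism involving disrupting the colonic barrier and intestinal microbiota dysbiosis".

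**Exposure.** Under Procedures, the sleep-wake schedule is moved by 12 hours on Day 3. That size was chosen because the investigators had found the influence of misalignment to be greatest there. Three simulated night shifts follow, the Test Day 1 assessments are repeated on Test Day 2, and discharge is on Day 7.

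**Risks.** The safety section says "We have identified five key potential risks to human subjects in this study" and lists confidentiality, phlebotomy, sigmoidoscopy with biopsy, questionnaires and the in-lab study. Minimizing Risk covers these and adds a sixth item, psychological stress. For the in-lab stay (item 5) it names sleepiness, poor sleep, accidents and a temporary jet-lag-like state that can include stomach upset.

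**Leaving the study.** The Early Withdrawal section is one sentence: "Participants may withdraw at any time". On completion, item 5 of Minimizing Risk offers recovery sleep and a taxi home.

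**The concern.** Patients are chosen because their disease is quiet, then given an exposure that the study expects may disturb it. On the protocol's own reasoning, a rise in permeability measured at Test Day 2 could precede a flare that appears after the patient has gone home. The risk list does not mention this, and nothing visible arranges for anyone to ask about it.

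What is at stake is subject protection and the completeness of the safety record. The risk most specific to this study in its UC group has no named entry. Detection after discharge depends on the patient or the clinic raising it.

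**Working it through.** The plan gives no figure for flare risk, so the check compares passages and counts days.

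1. **Is UC worsening named as a risk?** Safety and Adverse Events announces five risks and lists five. Minimizing Risk has six items. None of them names flare or worsening of UC. Active disease appears in item 3 only as something the limited sigmoidoscopy can detect.

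2. **How long is a subject observed after the shift?** The shift is on Day 3 and discharge on Day 7: 7 − 3 = 4 days. If Test Day 2 falls on Day 5 or 6, the last planned endoscopy comes 5 − 3 = 2 to 6 − 3 = 3 days after the shift. The Day 5 or 6 placement is an assumption, because the schedule figure is not shown; the second catheter is placed on Day 5.

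3. **What is captured inside that period?** Worsening present by Test Day 2 should show in the endoscopic score and stool calprotectin. Vital signs are checked daily and blood is drawn to Day 7.

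4. **What is scheduled afterwards?** I compared each provision that might serve.
   - The rapid visit by the study gastroenterologist (Minimizing Risk, item 3) belongs to the sigmoidoscopy complication plan and concerns bleeding and perforation.
   - The call to the study physician for distress (item 6) applies during the stay.
   - Return of the actigraphy watch (Payment to Participants) may come after discharge but is not a clinical assessment.
   - The safety board meets every six months and reviews study data. It does not contact patients.

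   Scheduled clinical contacts described after discharge: 0. After early withdrawal: 0.

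5. **Can an exposed subject leave before Test Day 2?** Yes. Item 5 foresees withdrawal by a subject who cannot stay awake during scheduled wake time. Such a subject could miss the second endoscopy and the stool sample taken before it.

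6. **How many subjects?** Twenty UC subjects are planned. Subject Recruitment reports that 70% of those passing screening complete, but does not say when leavers go, how many have UC, or whether 20 means enrolled or completed. I therefore estimate no number of leavers. The documents also give no flare rate and no lag from exposure to flare, so no expected number of flares can be derived.

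**The case against.** Four arguments on the other side carry weight.

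- **Silence is not a prohibition.** A reader might infer that a later flare would not be collected, or that the board would never see it. The documents do not support that. No visible text ends adverse-event reporting at discharge, and the board's safety remit is not limited to the stay. UC subjects also come from the site's own clinics, and the investigator specialises in IBD, so a flare could well become known. What stands is narrower: nothing is scheduled, so knowledge of a flare depends on spontaneous report or routine care.

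- **The hazard may be small.** The colitis and barrier evidence in the Objective and in Background A.4 and A.5 is mainly from long-running light-dark disruption, genetic disruption or established night work. Here there are three simulated shifts. Background A.3 also says environmental factors disrupt the barrier only in some people, and worse disease course belongs to the long-term objective. This stands, and it rules out reading the protocol as showing that these shifts cause flares.

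- **Item 5 already covers the in-lab exposure.** It does so in general terms, and its text admits effects lasting several days after the stay. But those effects are jet-lag symptoms, and worsening of the underlying disease is not among them.

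- **Material is missing.** Consent pages and the schedule figure were not available. A warning to patients may well sit in the consent form, so no claim is made that subjects are uninformed. A scheduled study assessment, however, would naturally be in the protocol body.

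Entry safeguards are also real: inactive disease, stable medication and more than 3 months without flare.

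**Conclusion.** The concern holds as a safety-planning gap. The protocol treats UC worsening as a foreseeable effect of misalignment, does not name it among the risks, and schedules no clinical contact after discharge or after withdrawal following the shift. It bears on 20 planned UC subjects. The consequence arises only for one who worsens after Test Day 2 or who leaves before it.

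The size of the risk cannot be given. It is plausible on the protocol's own argument but unquantified for a short exposure. No primary estimate, power figure or test is affected. The conclusion rests on the visible text, so a follow-up contact shown only in the missing material would change it.

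**What to change.** 1. Under in-lab risk item 5, in both the list and the mitigation text, name worsening of UC as a potential risk.
2. Add one remote repeat of the Mayo symptom items for each exposed UC subject. The instrument is already in use at entry: "All UC subjects will complete a validated questionnaire regarding disease-specific symptoms (Mayo Score").
3. Fix a single time for it before enrolment, for example one point between 2 and 4 weeks after discharge. That range is an assumption, because the protocol gives no lag; the investigators should choose and justify the time.
4. Include subjects who withdraw after the Day 3 shift, if they agree to be contacted.
5. Record the result as a safety outcome, refer any worsening to the study gastroenterologist, and report it to the existing board.

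**Cost.** A short addition to the risk text and one brief call per UC subject: 20 × 1 = 20 calls as planned. No new procedure is needed. The limits are that a single contact sees one point in time and that there is no unexposed UC group. A flare could be recorded and managed but not attributed to the exposure.
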